8.4. LABORATORY EVALUATIONS

Laboratory assessments include:

Hematology: complete blood count, reticulocytes, platelets and differential

Clinical chemistry: glucose, calcium, albumin, total protein, sodium, potassium, CO₂, chloride, phosphate, BUN [blood urea nitrogen], serum creatinine, uric acid, ALP, ALT, AST, LDH, CRP, and total and direct bilirubin

Coagulation: prothrombin time, INR, aPTT, fibrinogen.

Urinalysis: pH, specific gravity, protein, glucose, ketones, nitrite, leukocyte esteras

All clinical laboratory parameters will be converted to consistent units according to the International System of Units (SI) before summarization.

For numeric laboratory parameters, the observed values at each scheduled visit and change from baseline to post-baseline scheduled visits will be summarized. For numeric laboratory parameters that have an upper and/or lower reference range, all assessments (including unscheduled) will be categorized as low, normal, or high (i.e., below, within, or above reference range) and shift tables from baseline to max and min post-baseline values will be tabulated.

For categorical laboratory parameters, shift tables from baseline to max and min post-baseline values will be tabulated.

The incidence of grade 3 and 4 laboratory abnormalities will be summarized by CTCAE toxicity grade.

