4 PATIENT POPULATION

The study will enroll adult or adolescent patients with advanced solid tumors or lymphomas who are expected to have WT TP53 and are refractory to or intolerant of standard therapy, or for whom no standard therapy exists. The distinct inclusion/exclusion criteria for each cohort are presented in the remainder of this section.

4.1 Inclusion Criteria – Phase 1 dose escalation (ALRN-6924 administered as single agent therapy)

Patients must meet all of the following criteria to be considered for participation in this study:

1. Male or female patients age 18 years and older, inclusive, at the time of informed consent
2. Histologically- or cytologically-confirmed solid tumors that are metastatic or unresectable or lymphomas. Standard measures do not exist or are no longer effective for these patients.
3. WT TP53 status for relapsing or treatment-refractory solid neoplasms and lymphomas is mandatory for patients enrolling at Dose Level 4 and higher in Stage 1 of the DEP as well as for all patients enrolled in Stage 2 of the DEP or in the EXP. In EXP, beginning with Amendment 6, TP53 status still must be determined by the central laboratory, but confirmation of WT TP53 status is not required for enrollment or initiation of study treatment, if the Investigator deems it clinically unacceptable to delay treatment.
4. At least one target lesion that is measurable by RECIST 1.1 in patients with solid tumors or by IWG (2014) criteria in patients with lymphoma.
5. ECOG performance status 0-1
6. Predicted life expectancy of ≥ 3 months
7. Adequate hematologic bone marrow function, measured within 7 days prior to the first dose of ALRN-6924, defined as:
 - ANC $\geq 1.5 \times 10^9/L$
 - Hemoglobin $\geq 9.0 \text{ g/dL}$
 - Platelets $\geq 100 \times 10^9/L$
8. Adequate hepatic function, measured within 7 days prior to the first dose of ALRN-6924, defined as:
 - In the absence of disease involvement in the liver: bilirubin ≤ 1.5 times institutional ULN as well as AST and ALT ≤ 2.5 times ULN
 - In the presence of disease involvement in the liver: bilirubin ≤ 2 times ULN as well as AST and ALT ≤ 5 times ULN
9. Adequate renal function, measured within 7 days prior to the first dose of ALRN-6924, defined as:
 - Urinalysis with no evidence of +2 or higher proteinuria

- Serum creatinine \leq 1.5 times institutional ULN or calculated creatinine clearance \geq 50 mL/min (Cockcroft-Gault formula)

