5.7.1 Dose Levels for the Dose Escalation Portion of the Study

In the Dose Escalation portion of the study, increasing dose levels of ALRN-6924 will be evaluated in cohorts of 3-6 DLT-evaluable patients per dose regimen. Patients enrolled in Cohort 1 receive ALRN-6924 at Dose Level 1 (0.16 mg/kg). Based on allometric scaling, at 0.16 mg/kg dose in humans, the predicted AUC (50 $\mu\text{g}\cdot\text{hr}/\text{mL}$) is approximately 9% of the rat AUC at STD_{10} and approximately 6% of the AUC at the monkey HNSTD as described in Section 1.4.

In the absence of DLT in >33% of DLT-evaluable patients in either DR, subsequent cohorts of 3 to 6 patients will receive escalated doses until the MTD or an OBD is established for each dose regimen.

A 2-stage dose escalation design will be employed. During the initial Stage 1 Escalation Phase, 100% dose increments will be utilized until ≥ 1 of 3 patients in a cohort experiences any Grade ≥ 2 AE that is at least possibly related to study drug. Study drug-related AEs Grade ≥ 2 occurred in DL-4A (fatigue) and in DL-3B (neutropenia). Therefore, per protocol, Stage 2 has been implemented for subsequent dose escalations starting with DL-5A and DL-4B. Dose escalation will continue using 3-patient cohorts and the modified Fibonacci sequence (i.e., 67%, 50%, 40%, 33%), until the MTD or an OBD is established. As two DLTs have occurred in DR-7A (hypotension and hepatobiliary laboratory abnormalities), there will be no further dose escalation in DR-A. A new modified infusion regimen was tested (DR-A-2) starting at dose level 7A-2 (=4.4 mg/kg body-weight). As two DLTs have occurred in DR-7A-2 (anemia and neutropenia), there will be no further escalation in DR-A-2.

Figure 9: Dose Level and Dose Regimen Schematic

The observation of DLT(s) will be used to make individual patient determinations regarding dose reductions, interruptions or discontinuation throughout the course of the trial, but DLTs occurring during Cycle 1 will be used to inform safety and tolerability assessments for dose escalation decisions.

If DLTs are observed in the first cohort, the dose will be de-escalated to Dose Level -1. If DLTs are observed at Dose Level -1, the dose will be de-escalated to Dose Level -2. If DLTs are observed at Dose Level -2, other dose levels may be considered and implemented after discussions among the Investigators and Sponsor's Medical Monitor.

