3. GENERAL CONSIDERATIONS

3.1. GENERAL METHODS

- This Statistical Analysis Plan (SAP) addresses the analysis methodology for the Phase 1 (dose escalation) portion of this study.
- Separate analysis plans will be developed for analyses of
 - Phase 2a (dose expansion)
 - Pharmacokinetics
 - Pharmacodynamics
 - Cell-free DNA from blood
 - Immunogenicity
- All tabulations of data will be provided by dose cohort within each dose regimen, dose regimen overall, and overall for all subjects in the analysis set.
- Two versions of the 28-day dosing cycle (Dose Regimen A and Dose Regimen A2 as described in the protocol) were implemented in the study, but all analyses will combine these subjects.
- In addition to the tabulations delineated in analysis methods below, all data will be displayed in listings organized by regimen and dose cohort.
- The continuous variables will be summarized using number of observations (n), mean, standard deviation (SD), median, 95% confidence interval of the mean, minimum, and maximum, unless otherwise specified. All mean and median values will be formatted to 1 more decimal place than the measured value. All SD values will be formatted to 2 more decimal places than the measured value. Minimum and maximum values will be presented to the same number of decimal places as the measured value.
- The categorical variables will be summarized using frequency counts and percentages of subjects. Percentages will be calculated using the study population, excluding subjects with missing values, as the denominator. All percentages will be rounded to 1 decimal place. Number and percentage values will be presented as xx (xx.x).

Version V.1

- P-values will be output in the format: “0.xxx”, where xxx is the value rounded to 3 decimal places. Any p-value less than 0.001 will be presented as <0.001. If the p-value should be less than 0.0001, then present as <0.0001. If the p-value is returned as >0.999 then present as >0.999.
- Confidence intervals (CIs) will be presented as 2-sided 95% CIs unless specified differently in specific analyses.
- All analyses will be performed using SAS® statistical software package, version 9.3 or higher.

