3.4. VISIT WINDOWS

All collected lab, vital, and ECG data, including unscheduled visits, will be included in data listings and factored into data analyses though no relabelling of assessments based on visit windows will be instituted. Instead, for summaries by time point, only scheduled assessments will be tabulated according to the visit designations established by investigative sites and cleaned by data management. For shift analyses between baseline and maximum or minimum post-baseline assessments, all assessments, including unscheduled visits, will be included in the identification of extreme values.

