8.3. ADVERSE EVENTS

Treatment-emergent adverse events (TEAEs) are defined as AEs that are newly occurring or worsening on or after the date of the first dose of ALRN-6924. Reported AE terms will be coded using MedDRA version 19.1 or later.

The number and percent of subjects, and the number of events where relevant, will be summarized by SOC and PT for the following categories of TEAEs:

- All TEAEs
- Grade 3 or higher CTCAE grade TEAEs
- Related TEAEs defined as at least possibly related, as delineated by the investigator, or missing
- Serious TEAEs

- Serious related TEAEs
- TEAEs leading to discontinuation of study drug
- TEAEs leading to death

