8.7. ECOG PERFORMANCE STATUS

The ECOG performance status scores range from 0 to 5 as follows:

Grade	Description
0	Fully active, able to carry on all pre-disease performance without restriction
1	Restricted in physically strenuous activity but ambulatory and able to carry out work of a light or sedentary nature (e.g., light house work, office work)
2	Ambulatory and capable of all self-care but unable to carry out any work activities; up and about more than 50% of waking hours
3	Capable of only limited self-care; confined to bed or chair more than 50% of waking hours
4	Completely disabled; cannot carry on any self-care; totally confined to bed or chair
5	Dead

Source: Oken et al, 1982.

Shifts in ECOG performance status between baseline and the worst overall assessment will be summarized.

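### SAP 8.4 shows no shift when an already out-of-range laboratory value worsens in the same direction, Grade 1-to-2 worsening is in no laboratory count, and SAP 8.3 separates only Grade 3 or higher TEAEs

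*SAP*

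**What the plan says.** SAP 8.4 plans three outputs for numeric laboratory results:

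- Values and changes from baseline at scheduled visits, using the SAP 3.1 statistics, which include minimum and maximum.
- Shift tables from baseline to the highest and lowest post-baseline value, for which "all assessments (including unscheduled) will be categorized as low, normal, or high" against the reference range.
- A count of severe abnormalities: "The incidence of grade 3 and 4 laboratory abnormalities will be summarized by CTCAE toxicity grade".

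Categorical parameters such as dipstick urinalysis have their own shift tables and are not at issue. For shift analyses SAP 3.4 states that "all assessments, including unscheduled visits, will be included in the identification of extreme values", while by-visit summaries use scheduled assessments only. SAP 3.1 adds that "All tabulations of data will be provided by dose cohort within each dose regimen, dose regimen overall, and overall", and it promises listings of all data.

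SAP 8.3 tabulates TEAEs by system organ class and preferred term in seven categories. Only one is defined by grade: "Grade 3 or higher CTCAE grade TEAEs". Protocol 7.3, in its current form, commits to summarizing every toxicity by CTCAE 4.03 severity and by relationship to treatment. SAP 11 says the SAP was written against Amendment 6 and names one addition, duration of clinical benefit.

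Protocol 4.1 lets Phase 1 patients enter with AST and ALT up to 2.5 times ULN and bilirubin up to 1.5 times ULN. The clause beginning "In the presence of disease involvement in the liver: bilirubin" raises those limits to 5 times ULN for AST and ALT and 2 times ULN for bilirubin.

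**The concern.** A three-level category cannot register movement within its outer levels. A patient who starts high and goes higher is tabulated high-to-high, and one who starts low and goes lower is tabulated low-to-low. The eligibility rules make such starting points possible. The graded count that might compensate begins only at Grade 3.

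Safety and tolerability is a Phase 1 primary objective (protocol 2.1.1). Marrow and hepatobiliary laboratory changes were among the dose-limiting events (protocol 5.7.1 and 5.7.2). The protocol also works at the boundary between Grades 1 and 2: under 5.8.1, a toxicity that delays dosing counts as resolved once it is back to Grade 1 or lower, or to baseline. No table in SAP 8.3 or 8.4 counts the patients who crossed that boundary, or shows the grade from which they started.

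**Working it through.** There is no sample size or power figure to reproduce. The check sets the planned outputs against every possible worsening step.

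**Inputs.** Shift categories and the Grade 3-4 count come from SAP 8.4, and entry limits from protocol 4.1. The documents cite CTCAE 4.03 but do not print its cut-offs. I assume that Grade 0 is within range and that Grades 1 to 4 lie outside it in one direction.

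**Rule.** For baseline grade b and worst grade w, with b < w ≤ 4, a shift shows only if b = 0. The Grade 3-4 incidence registers the patient only if w ≥ 3.

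| b to w | Shift shown | In Grade 3-4 count |
|---|---|---|
| 0 to 1 | yes | no |
| 0 to 2 | yes | no |
| 0 to 3 | yes | yes |
| 0 to 4 | yes | yes |
| 1 to 2 | no | no |
| 1 to 3 | no | yes |
| 1 to 4 | no | yes |
| 2 to 3 | no | yes |
| 2 to 4 | no | yes |
| 3 to 4 | no | yes |

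**Result.** There are 4 + 3 + 2 + 1 = 10 steps. Four show a shift and 10 - 4 = 6 do not. Five of the six reach Grade 3 or 4, so 6 - 5 = 1 step, Grade 1 to 2, is in no laboratory count. The 0-to-1 and 0-to-2 steps share one cell. The Grade 3-4 count gives no baseline grade, so 1-to-3 and 2-to-3 look alike.

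**Sensitivity to entry grade.** The answer does not depend on the highest grade allowed at entry, provided Grade 1 is allowed:

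- Entry at Grade 0-1: 4 + 3 = 7 steps; 3 show no shift; 2 of those reach Grade 3-4; 3 - 2 = 1 remains.
- Entry at Grade 0-2: 4 + 3 + 2 = 9 steps; 5 show no shift; 4 of those reach Grade 3-4; 5 - 4 = 1 remains.

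**Which analytes.** For AST, ALT and bilirubin, the protocol alone shows that an above-range baseline is allowed. For example, AST moving from 2 to 4.9 times ULN is high-to-high. If Grade 3 begins above 5 times ULN (an assumption), that patient is in no laboratory count. Hemoglobin may enter from 9.0 g/dL. With an assumed lower limit of normal between 11.5 and 13.5 g/dL, the entry band already labelled low is 11.5 - 9.0 = 2.5 to 13.5 - 9.0 = 4.5 g/dL wide. Platelets may enter from 100 × 10⁹/L, which is also below usual lower limits (an assumption).

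**With a grade-shift table.** Each of the 10 steps has its own cell, and the number of steps in no count falls from 1 to 0. With two or three baseline grades and five worst grades, the table has 2 × 5 = 10 or 3 × 5 = 15 cells per analyte. Cohorts have 3 to 6 patients (protocol 5.7.1), and about 75 subjects are planned for escalation (SAP 2.2).

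**The case against.** The strongest reply is that what remains is narrow and mostly visible elsewhere. Under protocol 8.3, a laboratory change becomes an AE if the investigator finds it clinically significant, if it needs intervention, or if it alters dosing; it then enters the TEAE tables. By-visit summaries show minimum, median and maximum by cohort, and in a cohort of three these are all three patients' values. In Cycle 1 of Regimen A escalation, hematology is scheduled on Days 1, 2, 3, 8, 15, 16 and 22 (Appendix C). A reader might therefore infer too much from the gap by saying that only listings show Grade 2 laboratory values, or that worsening from an abnormal baseline is lost altogether. Neither is so: the extremes are displayed, and anything reaching Grade 3 or 4 is counted. What stands is that by-visit summaries omit unscheduled values and do not pair baseline with worst value. A Grade 2 event reported as a TEAE also appears without its grade.

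A second tempting reading links the gap to escalation, because the protocol records that drug-related events of Grade 2 or higher "occurred in DL-4A (fatigue) and in DL-3B (neutropenia). Therefore, per protocol, Stage 2 has been implemented for subsequent dose escalations". The documents do not support that link. The trigger concerned related AEs and had already operated. Escalation is decided by the Safety Review Committee, not from SAP tables, and a laboratory grade table carries no attribution. DLTs are Grade 3 or higher by definition (protocol 5.9.2) and have their own summary in SAP 8.2.

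The protocol mismatch also has limits. The wording of 7.3 under Amendment 6 cannot be seen, and all TEAEs beside Grade 3 or higher TEAEs is a severity split, if a coarse one. It does not, however, deliver a severity summary in any useful detail, and related TEAEs are not split by grade at all.

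**Conclusion.** The point holds as a reporting gap. Low/normal/high shift tables show no shift for same-direction worsening from an out-of-range baseline. Worsening to Grade 3-4 is still counted, without baseline grade. Grade 1-to-2 worsening is in no laboratory count, and 0-to-1 is not separated from 0-to-2. No other planned output counts patients by baseline and worst grade. In SAP 8.3 the only division by grade is at Grade 3, which is coarser than the current protocol 7.3 leads one to expect; whether it departed from Amendment 6 cannot be judged.

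The size is stated in grade steps: 1 of 10 uncounted and 6 of 10 without a shift, assuming Grade 1 begins at the reference limit. These are possibilities, not frequencies. The documents do not say how many patients entered out of range, so no patient number follows. DLT counts, the MTD and the selected 3.1 mg/kg dose are unaffected.

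**What to change.** In SAP 8.4, add a shift table from baseline CTCAE grade to worst post-baseline CTCAE grade, with unscheduled values included as SAP 3.4 already requires for shifts. Cover platelets, hemoglobin, neutrophils, AST, ALT and bilirubin. Keep the low/normal/high table. Read the new table mainly by regimen and overall, because cells will be sparse in cohorts of 3 to 6.

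In SAP 8.3, tabulate all TEAEs and related TEAEs by maximum CTCAE grade. This would meet the current protocol 7.3 and show related Grade 2 events as such.

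The cost is SAP wording and modest programming. The values are already collected, and grading is already needed for the Grade 3-4 count; it would be extended to baseline and to Grades 0 to 2. The layout has precedents in the SAP: for ECGs in 8.6, and in 8.7, where "Shifts in ECOG performance status between baseline and the worst overall assessment will be summarized". Sparse cells at cohort level are the only real drawback.

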8.5. VITAL SIGNS

Vital signs (respiratory rate, temperature, blood pressure, and heart rate) are assessed periodically during and after each infusion. The data analysis of these data will consist of two phases:

- For cycles 1 and 2, each subject's values at each time point and the changes from pre-infusion to each follow-up assessment within the cycle will be summarized.

- For cycle 3 and beyond, the average of each subject's values for each time point across cycles and the changes from pre-infusion average to each follow-up time point average will be summarized.

Additionally, the changes from baseline to max and min post-baseline values will be summarized.

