¹⁵This visit will be performed for all patients in DEP and performed in EXP only if the patient has experienced any grade 3 neutropenia, anemia or thrombocytopenia while on study, regardless of the relationship to ALRN-6924

APPENDIX D: Dose Regimen A and A-2 - Study Activities Cycle 2 and Beyond - ALRN single agent therapy

	Day 1 ¹ ±3 d		Day 8 ±1 d		Day 15 ±1 d		Day 16 ⁸ ±2 d	At the end of cycles 2, 4, 6, etc.	End-of-Treatment 30 ± 5 d after last dose or at study withdrawal	Long-Term Follow Up (EXP only) ¹⁶
	Pre-dose	Post-dose	Pre-dose	Post-dose	Pre-dose	Post-dose				
Serum or urine pregnancy									X	
Vital signs ²	X	X	X	X	X	X	X		X	
Physical exam ³	X		X		X				X	
12-lead ECG ⁴	X	X							X	
Laboratory assessments – chemistry ⁵	X				X		X		X	
Laboratory assessments – hematology ⁵	X		X		X		X		X	
Laboratory assessments – coagulation ⁵	X				X		X		X	
Laboratory assessments – urinalysis ⁵	X				X		X		X	
Laboratory assessments – CRP, fibrinogen	Cycle 2 only				Cycle 2 only		Cycle 2 only			
Collection of blood for immunogenicity ⁶	Cycle 2, 3, 5 only								X	
Blood Collection - PK assessments					Cycle 2 only ⁷	Cycle 2 only ⁷	Cycle 2: DEP only ⁷			
Blood Collection - cell-free DNA ⁶	Cycle 5 only								X	
ECOG Performance status ⁹	X		X		X				X	
Biopsy for biomarker assessments /p53 status ¹⁰							X		X	
Tumor Assessment/Imaging ¹¹								X	X ¹²	
ALRN-6924 dosing ¹³	X		X		X					
Concomitant medications ¹⁴	X	X	X	X	X	X	X		X	
AE assessment ¹⁵	X	X	X	X	X	X	X		X	
Phone calls or other contact										X

¹ “Day 29” = Day 1 of next cycle for patients continuing treatment. Day 1 pre-dose evaluations for Cycle 2 and subsequent cycles are to be done within 3 days prior to next cycle drug administration.

² Blood pressure, pulse, respiration rate, body temperature. For patients on > 1 year, this procedure is no longer a mandatory study procedure:

On the days of drug administration (Days 1, 8, 15 of each cycle) vital signs will be recorded pre-dose (within 30 minutes prior to SOI) and at the following timepoints:

During infusion:

DR-A (one hour infusion): 15 min (\pm 3 min) and 30 min (\pm 3 min)

DR-A-2 (two hour infusion): 30 min (\pm 3 min) and 60 min (\pm 3 min).

Post-infusion: At EOI (\pm 5 min) and as clinically indicated following EOI. In cycle 2 only, vital signs will be collected at 1 hr (\pm 5 min), 2 hrs (\pm 10 min) and 4 hrs (\pm 10 min) following EOI. Additional vital signs will be collected at the discretion of the investigator.

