APPENDIX F: Dose Regimen B - Study Activities Cycle 2 and Beyond

	Day 1 ¹ ±3 d		Day 3 EXP only ⁹	Day 4 and 8 ±1 d		Day 11 ±1 d		Day 12 ¹⁵ DEP only	Day 15 ¹⁶ EXP only	After last dose in cycles 3, 6, 9 etc.	End-of- Treatment 30 + 5 d after last dose or at study withdrawal	Long- Term Follow Up ¹⁷ (EXP only)
	Pre- dose	Post- dose		Pre-dose	Post-dose	Pre-dose	Post-dose					
Serum or urine pregnancy												X
Vital signs ²	X	X		X	X	X	X	X	X			X
Physical exam ³	X			X		X						X
12-lead ECG ⁴	X	X										X
Laboratory assessments – chemistry ⁵	X					Starting at Cycle 4		X	X			X
Laboratory assessments – hematology ⁵	X			X		Starting at Cycle 4		X	X			X
Laboratory assessments – coagulation ⁵	X							X				X
Laboratory assessments – urinalysis ⁵	X							X				X
Laboratory assessments – CRP, fibrinogen	Cycle 2 only					Cycle 2 only		Cycle 2 only				
Collection of blood for immunogenicity ⁶	Cycle 2, 3, 5 only											X
Blood Collection - PK assessments						X ⁷	X ⁷	X ⁷				
Blood Collection- cell-free DNA ⁶	Cycle 5 only											X
ECOG Performance status ⁸	X			X		X						X
Biopsy for biomarker assessments /p53 status			Day 3 or 10 ⁹					X ⁹				X ⁹
Tumor Assessment/Imaging										X ¹⁰	X ¹¹	

	Day 1 ¹ ±3 d	Day 3 EXP only ⁹	Day 4 and 8 ±1 d	Day 11 ±1 d	Day 12 ¹⁵ DEP only	Day 15 ¹⁶ EXP only	After last dose in cycles 3, 6, 9 etc.	End-of- Treatment 30 + 5 d after last dose or at study withdrawal	Long- Term Follow Up ¹⁷ (EXP only)
ALRN-6924 dosing ¹²	X		X	X					
Concomitant medications ¹³	X	X	X	X	X	X	X	X	
AE assessment ¹⁴	X	X	X	X	X	X	X	X	
Phone calls or other contact									X

¹ “Day 22” = Day 1 of next cycle for patients continuing treatment. Day 1 pre-dose evaluations for Cycle 2 and subsequent cycles are to be done within 3 days prior to next cycle drug administration.

² Blood pressure, pulse, respiration rate, body temperature. On the days of drug administration (Days 1, 4, 8, and 11 of each cycle) vital signs will be recorded pre-dose (within 30 minutes prior to SOI) and at the following timepoints:

(During infusion) 15 min (± 3 min) and 30 min (± 3 min);

(Post-infusion) At EOI (±5 min) and as clinically indicated following EOI. For patients on > 1 year, this procedure is no longer a mandatory study procedure.

In cycle 2 only, vital signs will be collected at 1 hr (±5 min), 2 hrs (±10 min) and 4 hrs (±10 min) following EOI. Additional vital signs will be collected at the discretion of the investigator.

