3.3. MISSING DATA

No imputation or extrapolation will be implemented for missing safety or clinical activity results. Partial start/end dates for AEs and medications will be handled as follows:

Adverse events:***Missing day of AE start date***

- AE will be treated as treatment emergent unless the month/year are strictly before the month/year of first dose.

Missing day and month of AE start date

- AE will be treated as treatment emergent unless the year is strictly before the year of first dose.

Missing day, month, and year of AE start date

- AE will be treated as treatment emergent.

Missing any date component of AE end date

- No imputation is needed.

Medications other than study treatment:

Missing any date component of medication start date

- No imputation is needed.

Missing day of medication end date

- Medication will be treated as concomitant unless the month/year are strictly before the month/year of first dose.

Missing day and month of medication end date

- Medication will be treated as concomitant unless the year is strictly before the year of first dose.

Missing day, month, and year of medication end date

- Medication will be treated as concomitant.

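### From Cycle 3, SAP 8.5 takes vital-sign change as the difference of two separate averages, with no rule that both come from the same infusions

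*SAP*

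**What the plan says.** SAP 8.5 handles vital signs in two ways. For Cycles 1 and 2, "the changes from pre-infusion to each follow-up assessment within the cycle will be summarized". From Cycle 3 it summarizes "the average of each subject's values for each time point across cycles and the changes from pre-infusion average to each follow-up time point average".

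Two general rules bear on incomplete data. SAP 3.3 states: "No imputation or extrapolation will be implemented for missing safety or clinical activity results". SAP 3.4 states that "for summaries by time point, only scheduled assessments will be tabulated according to the visit designations established by investigative sites". Neither rule, nor 8.5 itself, says that a pre-infusion value counts only if the same infusion also has the follow-up value.

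The SAP "addresses the analysis methodology for the Phase 1 (dose escalation) portion of this study", so the schedules that matter are Protocol Appendix D (DR-A and DR-A-2) and Appendix F (DR-B), footnote 2 in each:

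- At every infusion day from Cycle 3 the set is a pre-dose reading, two readings during the infusion and one at the end of infusion (EOI).
- Later readings are not fixed. For DR-A and DR-A-2, vital signs are taken at EOI "and as clinically indicated following EOI. In cycle 2 only, vital signs will be collected at 1 hr" and at the other listed hours. For DR-B they are taken at EOI and then "as clinically indicated following EOI. For patients on > 1 year, this procedure is no longer a mandatory study procedure".
- Appendix D has the same relaxation: "For patients on > 1 year, this procedure is no longer a mandatory study procedure".

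Protocol 3.2 expects that some dose-escalation patients may stay on treatment for 2 years or longer.

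**The concern.** A change from pre-infusion is meant to isolate what the infusion does to blood pressure, pulse, respiration and temperature. It does so if each follow-up reading is set against the pre-infusion reading of the same infusion. If the two averages are formed separately and some infusions supply only one of them, the difference also contains any contrast between the infusions that were fully recorded and those that were not. That contrast can come from slow drift over months of treatment, or from readings being taken because the patient was unwell that day.

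At stake is the readability of one table: the only planned vital-sign summary that measures change from pre-infusion after Cycle 2. The other planned summary, from baseline to the maximum and minimum, uses the last value before the first dose as its reference (SAP 3.2.1.1), so it does not isolate the infusion.

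**Working it through.** The documents state no figure for this point, so there is nothing to reproduce. The check compares two per-subject estimators:

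- (a) SAP 8.5: mean of follow-up values over infusions that have one, minus mean of pre-infusion values over infusions that have one.
- (b) Paired: mean of (follow-up − pre-infusion) over infusions that have both.

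**Complete pairs.** Over the same infusions, the mean of the differences equals the difference of the means. In a simulated subject with 33 complete infusions both gave −5.437 mmHg. Only incomplete pairs matter.

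**Infusion counts**, from the stated schedules and 365 days per year:

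- DR-A (28 days, 3 infusions): 13 full cycles in year 1. Cycles 3 to 13 give 11 × 3 = 33 infusions; year 2 gives up to 13 × 3 = 39.
- DR-B (21 days, 4 infusions): 17 full cycles in year 1. Cycles 3 to 17 give 15 × 4 = 60; year 2 gives up to 17 × 4 = 68.

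**Route 1: partial recording after 1 year.** Assume no true infusion effect, n1 complete year-1 infusions, m year-2 infusions with only a pre-infusion reading, and a shift of D mmHg in the subject's level between years. Then (a) = −D × m/(n1 + m) and (b) = 0.

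| Regimen | Year-2 infusions with pre-infusion reading only | m/(n1 + m) | Size at D = 5 | Size at D = 10 |
|---|---|---|---|---|
| DR-A | 25% (m = 10) | 10/43 | 1.16 | 2.33 |
| DR-A | 50% (m = 20) | 20/53 | 1.89 | 3.77 |
| DR-A | 100% (m = 39) | 39/72 | 2.71 | 5.42 |
| DR-B | 25% (m = 17) | 17/77 | 1.10 | 2.21 |
| DR-B | 50% (m = 34) | 34/94 | 1.81 | 3.62 |
| DR-B | 100% (m = 68) | 68/128 | 2.66 | 5.31 |

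The sign is opposite to the drift. If each year-2 infusion has both readings or neither, (a) = (b). D and the missing shares are assumptions.

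**Route 2: readings after EOI on clinical indication, within year 1.** This applies only if such readings enter the table. Assume a reading at 3 of 33 infusions, with pre-infusion pressure 115 at those and 130 at the other 30, and a true within-infusion change of −5 (follow-up 110). The pre-infusion average is (30 × 130 + 3 × 115)/33 = 128.64. Then (a) = 110 − 128.64 = −18.64, and (b) = −5.0. With 6 of 33 infusions, the average is (27 × 130 + 6 × 115)/33 = 127.27, so (a) = −17.27 and (b) = −5.0.

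**Route 3: an infusion stopped early.** Assume one of 33 infusions lacks a follow-up value and its pre-infusion value differs by 10 mmHg from the others. The pre-infusion average moves by 10/33 = 0.3 mmHg.

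**The case against.** The strongest reply is that the documents do not show pairs actually breaking.

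- A reader might infer that making vital signs optional after 1 year by itself puts the two averages on different infusions. The documents do not support that. The footnotes release the whole procedure, pre-infusion and follow-up readings alike. A mismatch needs sites to keep some readings and drop others; nothing describes that practice, and the number of patients treated beyond 1 year is not given. This objection stands, and it makes Route 1 conditional.
- In year 1 the scheduled set through EOI is fixed, and SAP 3.4 restricts time-point summaries to scheduled assessments. That may keep readings taken on clinical indication out of the table. It stands in part: the SAP does not say how a reading at 1 or 2 hours after EOI is classed when a site takes it on indication, so Route 2 is neither established nor ruled out.
- Under Protocol 5.4.1.1 an infusion paused for a Grade 1-2 reaction is restarted if symptoms abate, so an EOI value will often exist. Route 3 is real but small.
- A reader might also infer that the table could mask the hypotension recorded as a DLT at level 7A. The documents do not support that either. Escalation decisions rest on Cycle 1 DLTs (Protocol 5.9.2), and for Cycles 1 and 2 the SAP already uses within-cycle changes. DLTs, adverse events, the maximum and minimum summary and full listings are all reported separately.
- The SAP follows Amendment 6, while the protocol reviewed carries Amendment 7 text. Whether the 1-year relaxation already existed when the SAP was written cannot be checked.

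None of this supplies a pairing rule, and the paired calculation gives the same answer whenever the objection is right that the data are complete.

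**Conclusion.** The point holds as a low-cost improvement to a descriptive safety table, not as a demonstrated error in results. As written, the Cycle 3+ rule measures the infusion effect only when each infusion contributes both readings; otherwise it mixes in between-infusion differences.

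The size cannot be taken from the documents. Under the Route 1 assumptions it is about 1 to 5 mmHg, and it is 0 when readings are taken or skipped as a set. Route 2 could distort more in a single subject (−18.6 against −5.0 in the example), but only if those readings are tabulated. No dose decision or efficacy result depends on this table.

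**What to change.** In SAP 8.5, for Cycle 3 and beyond:

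1. Compute the change from each infusion's own pre-infusion value to each follow-up time point.
2. Average these changes per subject over infusions that have both values.
3. Report the number of paired and unpaired infusions at each time point.
4. State whether readings after EOI taken on clinical indication are included, so that 8.5 and SAP 3.4 agree.

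This extends to later cycles the within-cycle change already used for Cycles 1 and 2. It costs a few sentences and a small programming change, needs no new data, and leaves the results unchanged where pairs are complete.

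The fix has one limit. An infusion with no follow-up value drops out of the paired change and remains visible only in the listings, the adverse event tables and the maximum and minimum summary. That is why the unpaired count should be shown.
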